### 4.4 **Premature Discontinuation**

### 4.4.1 Premature Discontinuation of Investigational Medicinal Product

Patients should discontinue the IMP if any of the following occurs:

- 1. The patient withdraws his/her consent to participate in the study.
- 2. The patient develops an illness that would interfere with his/her continued participation in the study, at the Investigator's discretion.
- 3. The patient is noncompliant with study procedures or medication, which in the opinion of the Investigator, impacts patient safety and/or the integrity of the study results.
- 4. The patient takes prohibited medication that warrants the IMP discontinuation at the discretion of the Investigator. The introduction of any standard of care PBC treatment (OCA, fenofibrate, or bezafibrate) is allowed, but warrants IMP discontinuation (see Section 6.7). Dose modifications of concomitant PBC treatments initiated before Randomization do not require IMP discontinuation.
- 5. The patient is confirmed to be pregnant.
- 6. The Sponsor or regulatory agency requests withdrawal of the patient.
- 7. The patient has suspected drug-induced liver injury (sDILI) meeting Criteria C in Appendix II.
- 8. The patient has CTCAE Grade ≥2 anemia AND the retest absolute reticulocyte count is below 50% of the Baseline value, IMP will not be resumed and will be permanently discontinued.

- 9. The patient has a retest TSH level of  $\geq 10$  mIU/L if overt biological hypothyroidism is confirmed (ie, TSH  $\geq 10$  mIU/L and reduced free T4) (see Section 5.3.2.3).
- 10. The patient has one or more adverse clinical outcome listed in Section 5.4.
- 11. The patient has a severe cardiac condition per the Investigator's judgment, QT prolongation (QTc Fridericia interval >450 milliseconds for males and >470 milliseconds for females), or an increase in QTc greater than 60 milliseconds from Baseline, whichever comes first.

Patients who permanently discontinue IMP prior to completion of the Week 24 Visit (Visit 8) will have an EoT Visit 30 days after the last IMP dose, after which every possible effort should be made to complete the Week 24 study assessments (Visit 8) (see Table 1).

Patients who discontinue IMP prematurely will not be replaced.

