#### 7.1.5 Adverse Events of Special Interest

The AESIs for this study are DILI, anemia, and hypothyroidism.

AESIs of DILI will be defined as any DILI event that meets the criteria in **A**, **B**, or **C** of Appendix II. Please refer to Section 5.3.2.1 and Appendix II for details regarding the detection and management of cases of DILI.

AESIs of anemia will be defined as CTCAE Grade  $\geq 2$  anemia AND absolute reticulocyte counts of <50% of the Baseline value, which is confirmed by repeat testing. Please refer to Section 5.3.2.2 for details regarding the detection and management of potential cases of bone marrow toxicity.

AESIs of hypothyroidism will be defined as TSH levels of  $\geq 10$  mIU/L, which is confirmed by repeat testing at the central laboratory (ie, TSH  $\geq 10$  mIU/L and reduced free T4). Please refer to Section 5.3.2.3 for details regarding the detection and management of hypothyroidism. The AESI should be reported by the investigative site to the ICON Drug Safety Center within 24 hours of learning about the event by completing the paper safety report form and sending it via email or fax. The documentation and processing of AESIs is further detailed in the Investigator Site File.

The AESIs will be adjudicated by the Adjudication Committee (see Section 9.4.1).

Investigators will indicate on the relevant Adverse Event eCRF page if the event meets the criteria for an AESI. If the event meets the criteria for an AESI, the Investigator will inform the Sponsor (or designee) of the AESI utilizing the safety report form (refer to the SAE contact information at the beginning of this protocol) and will then complete the Adjudication Event eCRF.

Please refer to the Investigator adjudication manual for further information.

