#### 8.4.2 Analysis of Safety

The safety endpoints are listed in Section 2.2.

The Safety Analysis Set will be used for the analysis of safety data (AEs, including AESIs, clinical laboratory tests, vital signs, 12-lead ECGs, and physical examination).

AEs that occur, having been absent before the date and time of the first dose of the IMP, or have worsened in severity or seriousness after initiating the IMP until 30 days after the date and time of last dose of IMP will be classified as treatment-emergent AEs (TEAEs). The number of TEAEs and number and percentage of patients experiencing TEAEs will be summarized by treatment group, severity, and relation to IMP. TEAEs will be summarized by Medical Dictionary for Regulatory Activities (MedDRA) system organ class (SOC) and preferred term. All AEs will be listed by patient.

SAEs will be listed by patients and summarized by treatment group, MedDRA SOC, and preferred term. Summaries will also be presented by severity and relationship to IMP.

Laboratory data (hematology, serum chemistry, and urinalysis) will be converted to Système International units for reporting and processing purposes. Absolute values and changes from Baseline will be presented descriptively. Laboratory data outside study-specific reference ranges will be listed. Abnormal laboratory values will be listed by patient and summaries of the incidence and frequency by treatment group, scheduled visit, severity, and relationship to IMP will be presented. Shift tables of CTCAE (version 4.03) graded labs will be presented. WBC and reticulocyte counts will be expressed in absolute values. Differential count will be expressed as both absolute count and percentage of WBCs. Evaluation of druginduced serious hepatotoxicity (eDISH) analysis will be conducted in order to explore potential liver toxicity signals by treatment group.

Vital signs and ECG parameters will be presented descriptively. Vital signs including pulse rate, SBP, and DBP and 12-lead ECG data will be summarized by treatment group and listed by patient.

A summary of abnormal physical examination findings by treatment group and scheduled visit will be presented.

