9.4 Exploratory Endpoints

- Changes in markers of liver fibrosis, as assessed by Enhanced Liver Fibrosis (ELF) score, PRO-C3 (released N-terminal propeptide of Type III collagen), C3M (a peptide of helical collagen Type III degradation), and PRO-C3/C3M ratio at Week 24 compared to Baseline
- Changes in total and conjugated bilirubin over 24 weeks compared to Baseline
- Changes in markers of bile acid metabolism, as assessed by total bile acids, C4 (C4=7α-OH-4-cholesten-3-one), fibroblast growth factor (FGF)19, and FGF21 over 24 weeks compared to Baseline
- Changes in markers of liver function over 24 weeks compared to Baseline, as assessed by:
 - o Serum fibrinogen, albumin, and international normalized ratio (INR)
 - Alanine aminotransferase (ALT), aspartate aminotransferase (AST), gamma glutamyl transpeptidase (GGT), high sensitivity C-reactive protein (hsCRP), and immunoglobulin M (IgM) indicating liver inflammation and injury
- Assessment over a 24-week period of:
 - All-cause mortality
 - Proportion of subjects requiring a liver transplant (transplant list inclusion)
 - Proportion of subjects with a Model for End Stage Liver Disease (MELD) score of ≥15
 - Proportion of subjects with new onset of variceal/portal hypertension bleed and/or hepatic encephalopathy (West Haven criteria), spontaneous bacterial peritonitis, and ascites requiring treatment
- Change over a 24-week period compared to Baseline in:
 - Social isolation symptoms, as assessed by the PBC-40 social domain
 - o Overall health-related quality of life, as assessed by the PROMIS-29 questionnaire
 - EuroQol 5-dimension (EQ-5D) Utility Index
- Predose plasma concentrations of setanaxib and GKT138184 over a 24-week period

Secondary and exploratory endpoints captured for subjects who entered the extension phase under protocol versions 1.0 to 4.0 are described in protocol V4.0.

Sponsor: Calliditas Therapeutics Suisse SA

Protocol No: GSN000350

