12.6.3 Laboratory Data

Laboratory data will be reported in Système International (SI) units.

Version Date: 27-June-2024

Sponsor: Calliditas Therapeutics Suisse SA

Protocol No: GSN000350

For clinical biochemistry, hematology and liver function tests (Table 8), shift tables from baseline to worst CTCAE grade on treatment will be produced for the SS, with separate summaries for each treatment period. Only parameters which have toxicity grading will be summarized. WBC and reticulocyte

counts will be expressed in absolute values. Differential count will be expressed as both absolute count and percentage of WBCs. Only central lab data will be included in the table summaries. All lab data collected locally and centrally will be listed.

Table 8: Laboratory Tests

Laboratory Tests	Parameters
Hematology	Hematocrit; hemoglobin; absolute and relative reticulocyte counts, red blood cell (RBC) count; white blood cell (WBC) count; differential WBC count; platelet count; absolute neutrophil count; mean cell volume, INR
Biochemistry	Glucose; total protein; creatinine; urea; total cholesterol; triglycerides; sodium; potassium; chloride
Liver Function	Serum fibrinogen, albumin, ALP, ALT, AST, total and conjugated bilirubin, GGT, hsCRP, lgM

To further examine the liver function tests collected during the study, suspected drug-induced liver injury (sDILI) summaries will be produced. Proportion of subjects meeting any of the following criteria for any post-baseline assessments will be presented for the SS, for each treatment period:

- AST or ALT ≥3xULN
- AST or ALT >2xBaseline
- Total bilirubin >2xULN
- INR>1.5

Any subjects with any of the above criteria for sDILI or cholestasis will be flagged in the listings. Subjects at risk of a drug induced liver injury according to Hy's law will also be flagged. Hepatic function abnormality defined by an increase in AST and/or ALT to \geq 3xULN concurrent with an increase in total bilirubin to \geq 2xULN but without increase in ALP (i.e., ALP < 2xULN) meets the criteria for Hy's law and raises the concern for DILI.

The MELD score will be calculated by the central laboratory based on the results from the liver biochemistry (total bilirubin), biochemistry (creatinine), and hematology (INR) blood samples. Subjects with a MELD score of \geq 15 will be flagged in the listings.

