Data from the Extension Phase will be restricted to the period while a subject was on active and change from baseline comparisons using the extension baseline.

Table 9: Other Laboratory Tests

Laboratory Tests	Parameters
Markers of Liver Fibrosis	ELF score components for calculation of ELF score (TIMP-1, PIIINP, and hyaluronic acid) and the other PBC-related biomarkers (PRO-C3 and C3M; PRO-C3/CRM ratio)
Markers of bile acid metabolism	Total bile acids, C4, FGF19, FGF21
Autoantibodies	AMA titer, PBC-specific antibodies (anti-GP210, anti-SP100, antibodies against major M2 components [PDC-e2, 2-oxo-glutaric acid dehydrogenase complex])

Sponsor: Calliditas Therapeutics Suisse SA

Protocol No: GSN000350

Laboratory Tests	Parameters	
Viral Serology	HIV antibodies (1 and 2) and, if positive for HIV antibodies, HIV RNA; Hepatitis B surface antigen and hepatitis C virus antibodies and, if positive for HCV antibody, HCV RNA	
Pregnancy test	Serum pregnancy test; urine Pregnancy test	
Thyroid function	TSH and free T4	
Drug Screen (Urine)	Urine drug screen	
Urinalysis	pH; protein; glucose; ketones; bilirubin; blood; microscopic examination of the sediment	

Refer to Table 98, for a list of other laboratory parameters to be collected on this study and the laboratory test category each parameter will be summarized under. Autoantibodies, viral serology, pregnancy test, and drug screen parameters will be listed only. Markers of liver fibrosis, markers of bile acid metabolism, urinalysis, thyroid function will be summarized descriptively by scheduled visit using the SS.

Standard ranges from the central laboratory will be used for the laboratory analysis. The assessment as to if a lab test is low, high, normal as applicable will be derived using the standard ranges for central lab data. Laboratory data outside study-specific reference ranges will be listed.

Abnormal laboratory values, defined as values outside the normal range, will be listed by subject. Summaries of the incidence and frequency by treatment group and scheduled visit will be presented.

12.6.4 eDISH Analysis

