12.6.6 Physical Examinations, ECGs, and Other Observations Related to Safety

ECGs will be read centrally and ECG mean Heart Rate (HR), RR interval, PR Interval, QRS Duration, QT interval, QTcB interval and QTcF interval will be collected and summarized. In the Extension Phase, ECG may be read locally and HR, PR interval, RR interval, QRS interval, QT interval and QTcF interval will be listed. ECGs will be presented by the category normal, abnormal, unevaluable, and unknown for each assessment time point in the safety analysis, over the treatment period of 52 weeks. Shift plots of baseline as compared to highest and lowest on treatment value by treatment group will be presented for both treatment periods defined in Section 10.7.1. A listing of subjects ECG data will be provided.

QTc outliers are defined as QTc values following dosing that are greater than 450 msec or are increases from baseline greater than 30 msec. QTc outliers will be highlighted in the data listings, with subjects meeting the criteria at any time point listed separately. Outliers will be summarized using separate shift tables for each treatment period defined in Section 10.7for the following categories:

Version Date: 27-June-2024 Sponsor: Calliditas Therapeutics Suisse SA

Protocol No: GSN000350

Values ≤450 msec, >450-480 msec, >480-500 msec, >500 msec at baseline versus values ≤450 msec >450-480 msec, >480-500 msec, >500 msec post-dose

• Values ≤450 msec, >450-480 msec, >480-500 msec, >500 msec at baseline versus increase from baseline of ≤30 msec, >30-60 msec, >60-90 msec or >90msec post-dose

A summary of physical examination findings will be presented for each scheduled visits, showing the proportion of subjects with "Normal" and "Abnormal" physical examinations. The number of abnormal, clinically significant and not clinically significant assessments will be tabulated by scheduled visit using the SS and treatment period of 52 weeks. All physical examination findings will be provided in listings.

The Child-Pugh score and Child-Pugh classification of Severity of Cirrhosis as collected on the CRF page will be listed for all scheduled visits with flags to indicate in the value is treatment for each treatment periods defined in Section 10.7.1. The individual components required to calculate the Child-Pugh score and class will also be listed).

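### The SAP specifies no value or change-from-Baseline summaries for haematology, chemistry and liver tests, reticulocytes included, and no table counts women above the protocol's 470 ms QTcF limit

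*SAP*

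**What the plan says.** **Laboratory data.** Protocol 8.4.2 says of haematology, chemistry and urinalysis results: "Absolute values and changes from Baseline will be presented descriptively". SAP 12.6.3 groups haematology, biochemistry and liver function in Table 8 (Laboratory Tests). For these, "shift tables from baseline to worst CTCAE grade on treatment will be produced for the SS", and the restriction "Only parameters which have toxicity grading will be summarized" follows shortly after. By-visit description is named only for groups in the next table, Other Laboratory Tests: "Markers of liver fibrosis, markers of bile acid metabolism, urinalysis, thyroid function will be summarized descriptively by scheduled visit using the SS". The section also plans the incidence of out-of-range values by arm and visit, a count of subjects meeting liver-injury criteria (including AST or ALT above twice Baseline), and listings. SAP 6.1 amends a different sentence of the same protocol paragraph and does not mention this one.

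**Anaemia as an AESI.** Protocol 7.1.5 requires CTCAE Grade ≥2 anaemia together with "absolute reticulocyte counts of <50% of the Baseline value, which is confirmed by repeat testing".

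**Exploratory endpoints.** SAP 9.4 lists "Changes in markers of liver function over 24 weeks compared to Baseline, as assessed by" fibrinogen, albumin, INR, ALT, AST, GGT, hsCRP and IgM, and separately the change in total and conjugated bilirubin. SAP 12.5.5 then describes only MRE stiffness and patient-reported outcomes.

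**ECG.** SAP 12.6.6 states: "QTc outliers are defined as QTc values following dosing that are greater than 450 msec or are increases from baseline greater than 30 msec". Its shift tables cut at 450, 480 and 500 ms, and the change from Baseline at 30, 60 and 90 ms. QTcB and QTcF are both collected. Protocol 4.4.1 discontinues IMP for "QT prolongation (QTc Fridericia interval >450 milliseconds for males and >470 milliseconds for females", or for a rise of more than 60 ms. Exclusion criterion 17 uses the same sex-specific limits on centrally read QTcF.

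**The concern.** Protocol 1.1.3 names ECG changes, thyroid-hormone effects, and erythrocyte and reticulocyte effects as the treatment-related findings in dogs. The top dose here is twice the highest given earlier to patients with PBC. Protocol 3.2.1 puts expected exposure around the NOAEL, with a safety margin of 0.7 for the main metabolite. Protocol 1.2 intends to compare the benefit-risk of the two doses. The haematology and QT tables are where a dose-related shift would be sought.

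Grade tables and out-of-range counts register a change only when a value crosses a fixed boundary. They do not show a shift in an arm's mean, or a large fall from a patient's own Baseline that stays inside the range. For QT, a reader will want to know how many patients met the protocol's own criterion, and the planned bands do not give that number for women.

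**Working it through.** No sample size, power or alpha figure bears on this point, so there is no stated result to reproduce. The check is to map each protocol criterion to the SAP output that would show it.

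**1. By-visit laboratory summaries.** Within Table 8 (Laboratory Tests), only ALP has by-visit descriptive summaries specified elsewhere (SAP 12.5.2.1, as the primary endpoint). For the remaining haematology, biochemistry and liver tests, neither 12.5.5 nor 12.6.3 specifies values or changes by visit. By contrast, SAP 12.6.5 states both explicitly for vital signs.

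**2. Where a reticulocyte fall would appear.**

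| Pattern | SAP output |
|---|---|
| <50% of Baseline, confirmed, with Grade ≥2 anaemia | AESI tables (12.6.1) and adjudicated events (12.6.2) |
| Below the normal range | Out-of-range incidence by arm and visit (12.6.3), without the size of the fall |
| <50% of Baseline, within range, no Grade ≥2 anaemia | Listings only |
| Fall in an arm's mean, values within range | No table |

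Whether reticulocytes carry a CTCAE v4.03 grade is not stated in the documents. If they do, they enter the grade shift table, but change against the 50%-of-Baseline criterion is still not tabulated. Liver tests do get a table relative to Baseline.

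**3. QTc mapping.**

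| QTc (ms) | SAP band | SAP outlier | Over male limit | Over female limit |
|---|---|---|---|---|
| 455, 465, 470 | >450-480 | yes | yes | no |
| 471, 475, 480 | >450-480 | yes | yes | yes |
| 481 | >480-500 | yes | yes | yes |

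Every value over either limit exceeds 450, so none is missed. Within the >450-480 band, (470 − 450)/30 = 0.67 of the width lies at or below the female limit. The number meeting the absolute criterion (men >450 plus women >470) is at least the count above 480 and at most the count above 450. The table cannot narrow it further. The >60 ms rise falls exactly on a table cut (>60-90 and >90).

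**4. Scale.** Protocol 1.1.1 gives a 9:1 female-to-male ratio for the disease. If enrolment followed it (an assumption), 0.9 × 66 = 59.4 patients would be women, with a range of 0.9 × 60 = 54 to 0.9 × 70 = 63.

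**5. Illustration only; none of these means or SDs is in the documents.**
- The 95% half-width for an arm difference in mean reticulocyte change is t(0.975, 2n − 2) × SD × √(2/n). With n = 22 and SD 25%, this is about ±15 points (±12 at SD 20%, ±24 at SD 40%). With the 16 evaluable per arm that the plan expects and SD 25%, it is about ±18.
- For female QTcF with mean 415-425 ms and SD 15-20 ms, the normal tail above 450 ms runs from 0.010 (z = 35/15) to 0.106 (z = 25/20). Above 470 ms it runs from 0.0001 (z = 55/15) to 0.012 (z = 45/20).

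**The case against.** The strongest reply is that the SAP is incomplete here and does not contradict the protocol. The sentence about toxicity grading comes in the shift-table paragraph and most naturally limits those tables. The SAP is to be read with the protocol, and 6.1 does not withdraw Protocol 8.4.2. SAP 10.1.1 and 10.3 derive baselines and visit windows for these same liver tests, 10.1.5 gives change formulas, and section 12.0 sets default continuous summaries. By-visit tables may well have been intended. That reading is fair, but it leaves the gap: the tables are specified nowhere for this set, while they are specified for vital signs and for the other laboratory groups.

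A reader might infer that the safety tables cannot show a marrow or QT signal. The documents do not support that. Confirmed anaemia AESIs, adjudicated anaemia and out-of-range incidence are all tabulated. A 450 ms cut over-flags women and hides no one. The >60 ms rise has its own categories, QTcF is summarised, outlier subjects are listed separately, and adverse events leading to treatment discontinuation are tabulated. Because the bands form a baseline-by-post-dose table, women who enter above 450 ms have their own row, which narrows the mixing without removing it.

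A reader might also infer from the dog data that reticulocytes fall before red cells. Protocol 1.1.3 reports a fall of about 90% in one dog by Week 5 and no further haematology until Week 13. It does not give red-cell status at Week 5. Nor does the point extend to thyroid function: TSH and free T4 are already summarised by visit, and confirmed hypothyroidism is an adjudicated AESI.

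**Conclusion.** The point holds as a reporting gap with two parts.

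- **Laboratory tests.** A summary that the protocol promises is not specified in the SAP for the haematology, biochemistry and liver tests (ALP apart), and the omission is not declared. It covers reticulocytes, a named toxicology signal, and most of the liver-function endpoints in SAP 9.4. What is lost from tables is within-range change, including a fall below 50% of Baseline without Grade ≥2 anaemia. This rests on the SAP text as written. It does not depend on whether reticulocytes are graded.
- **QTc.** The number of women over the protocol's QTcF threshold cannot be read from any table, and women at 451-470 ms are labelled outliers although they are within the protocol limit. If the 9:1 ratio applies, this concerns most of the trial.

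The precision and tail figures are illustrative. At an SD of 40%, a 20% mean fall would not be distinguishable from zero, so a by-visit summary does not guarantee detection. The primary inference is unaffected, and the individual data remain in listings. The point takes no view on which clinical limit is right.

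**What to change.** 1. In SAP 12.6.3, add by-visit absolute values and change from Baseline for all parameters in Table 8 (Laboratory Tests), including absolute reticulocytes. State that these tables also serve the liver-function and bilirubin endpoints in SAP 9.4. If any of this is deliberately dropped, record it in SAP 6.1 as a departure from Protocol 8.4.2.
2. Add n (%) per arm with absolute reticulocytes below 50% of Baseline, with and without Grade ≥2 anaemia.
3. In SAP 12.6.6, define QTc outliers on centrally read QTcF. Add counts by sex and arm against the protocol's own thresholds (>450 ms men, >470 ms women) and the >60 ms increase. Keep the existing bands.

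The cost is SAP wording and a few standard tables from data already collected. No visit, sample or clinical rule changes.

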### 4.2 Exclusion Criteria

A patient who meets any of the following exclusion criteria will not be eligible for inclusion in the study:

- 1. A positive pregnancy test or breastfeeding for female patients.
- 2. Any historical or current hepatic decompensation event defined as variceal/portal hypertension bleed and/or hepatic encephalopathy, spontaneous bacterial peritonitis, ascites requiring treatment, or liver transplantation list inclusion.
- History of liver transplantation, current placement on a liver transplant list or current MELD score of ≥12 unless the patient is on anticoagulant therapy, or a Child-Pugh Score of ≥6.
- 4. Cirrhosis with complications, including history or presence of hepatocellular carcinoma.
- 5. Total bilirubin >2×ULN. In case of total bilirubin elevation >ULN the Screening serum albumin must be within the reference range.

One repeat blood sampling (with analysis by the central laboratory) can be performed at the discretion of the Investigator at Screening Visit 2 for patients who meet this exclusion criterion at Screening Visit 1. If this exclusion criterion is not met at Screening Visit 2, the patient may be eligible for the study.

6. Plasma ALT >3×ULN and/or AST >3×ULN.

One repeat blood sampling (with analysis by the central laboratory) can be performed at the discretion of the Investigator at Screening Visit 2 for patients who meet this exclusion criterion at Screening Visit 1. If this exclusion criterion is not met at Screening Visit 2, the patient may be eligible for the study. 7. INR >1.2 unless patient is on anticoagulant therapy.

One repeat blood sampling (with analysis by the central laboratory) can be performed at the discretion of the Investigator at Screening Visit 2 for patients who meet this exclusion criterion at Screening Visit 1. If this exclusion criterion is not met at Screening Visit 2, the patient may be eligible for the study.

- 8. Estimated glomerular filtration rate (eGFR) <30 mL/min/1.73 m^2, as calculated by the central laboratory using the chronic kidney disease epidemiology collaboration (CKD-EPI) equation.
- 9. TSH >ULN at Screening.

One repeat blood sampling (with analysis by the central laboratory) can be performed at the discretion of the Investigator at Screening Visit 2 for patients who meet this exclusion criterion at Screening Visit 1. If this exclusion criterion is not met at Screening Visit 2, the patient may be eligible for the study.

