#### 5.3.2.1 Suspected Drug-induced Liver Injury

During the study, the Investigator will remain vigilant for increases in liver biochemistry. The Investigator is responsible for determining whether the patient meets DILI criteria at any point during the study.

In the event that a patient has any of the following laboratory results, please refer to Appendix II for details regarding the detection and management of suspected or confirmed cases of DILI, including instructions for retesting, close monitoring, and action to take regarding the IMP:

- AST or ALT  $\geq 3 \times ULN$
- AST or ALT  $>2 \times$  Baseline
- Total bilirubin >2×ULN
- INR >1.5 (except for patients on anticoagulant therapy).

Baseline values for liver tests (ALT and AST) are determined by averaging the values obtained at Screening and Baseline/Day 1 to determine the arithmetic mean.

Details of the IMP stopping criteria relating to suspected or confirmed DILI are provided in Section 4.4 and Appendix II.

Any suspected or confirmed DILI events meeting the criteria for an AESI, as defined in Section 7.1.5, will be reported to the Sponsor (or designee) following the same procedure as for SAEs (see Section 7.4).

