10.0 Conventions and Derivations

10.1 Baseline and Change from Baseline

10.1.1 Baseline Values for Liver Biochemistry

Baseline values for liver biochemistry (ALP, ALT, AST, total and direct bilirubin, and GGT) are determined by the geometric mean of the last (up to) 3 measurements preceding the first administration of study drug. This includes unscheduled and screening visits. The formula for the geometric mean (GM) given three measurements a, b, and c is expressed as follows:

$$GM = \exp(\log(a) + \log(b) + \log(c)/3)$$

For subjects who have records for both Screening/Visit 1 and Baseline Visit 3, the baseline will be calculated as the geometric mean of these two values. If there is an additional unscheduled pre-dose result, the geometric mean will be calculated using up to three values.

For subjects who have records for Screening/Visit 1, Screening/Visit 2, and Baseline Visit 3, the Screening/Visit 1 result should be disregarded due to the subject's re-screening. The baseline should be calculated as the geometric mean of the Screening/Visit 2 and Baseline Visit 3 results. If there is an additional unscheduled pre-dose result, the geometric mean should include up to three values.

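### The SAP's suspected-DILI table and listing flag count INR >1.5 in anticoagulated patients, whom the protocol exempts from that criterion

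*SAP*

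**What the plan says.** Protocol 5.3.2.1 lists four laboratory results that send the investigator to Appendix II: AST or ALT at least 3×ULN, AST or ALT above 2×Baseline, total bilirubin above 2×ULN, and "INR >1.5 (except for patients on anticoagulant therapy"). Appendix II repeats that exemption in its retest list, in Criteria A and B, and in both INR items under Criteria C.

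Anticoagulated patients are foreseen at entry. Exclusion 7 in Protocol 4.2 reads "INR >1.2 unless patient is on anticoagulant therapy".

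SAP 12.6.3 states that "suspected drug-induced liver injury (sDILI) summaries will be produced". It lists the same four criteria in the same order, with the INR item shortened to INR >1.5, and tabulates them by treatment period for the Safety Set: "Proportion of subjects meeting any of the following criteria for any post-baseline assessments will be presented for the SS". It adds: "Any subjects with any of the above criteria for sDILI or cholestasis will be flagged in the listings". SAP 6.1, which records changes from the protocol, covers the per-protocol set and the abnormal-laboratory summaries, and does not mention this one.

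The baselines also differ. Protocol 5.3.2.1 says "Baseline values for liver tests (ALT and AST) are determined by averaging the values obtained at Screening and Baseline/Day 1", as an arithmetic mean. SAP 10.1.1 says that ALT and AST baselines "are determined by the geometric mean of the last (up to) 3 measurements preceding the first administration of study drug", unscheduled values included. The SAP gives no separate baseline for the suspected-DILI table.

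**The concern.** The SAP reproduces a protocol list almost item for item and loses one qualifier. Since the change is not declared, it reads as a transcription omission and not as a chosen method. The qualifier matters because a raised INR is the expected effect of some anticoagulants and, in such a patient, says little about liver injury.

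At stake is whether a table headed suspected DILI matches the rule that sites apply. DILI is one of three AESIs. Protocol 1.1.4 already reports four SAEs of mildly raised liver tests considered possibly related to study drug, so readers will look closely at the by-arm proportions. With about 22 patients per arm, one patient moves a proportion visibly.

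**Working it through.** The plan states no figure on this point, so there is none to reproduce. The check is a comparison of texts followed by simple arithmetic.

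**1. Criteria side by side**

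| Criterion | Protocol 5.3.2.1 | SAP 12.6.3 |
|---|---|---|
| AST or ALT | ≥3×ULN | ≥3×ULN |
| AST or ALT | >2×Baseline | >2×Baseline |
| Total bilirubin | >2×ULN | >2×ULN |
| INR | >1.5, anticoagulated patients exempt | >1.5, no exemption |

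**2. Who can be affected**

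Exclusion 7 lets anticoagulated patients in with an INR above 1.2. Exclusion 3 also bars a Child-Pugh score of 6 or more, and on its plain reading the anticoagulant exception there belongs to the MELD limit only. Section 5.1.4 calculates Child-Pugh from the screening INR. Appendix V gives 1 point for INR below 1.7 and 2 points for 1.7 to 2.3. With the other four items at their minimum of 1 point each, an INR of 1.7 scores 4 + 2 = 6, which excludes. Three routes into the table remain:

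- a screening INR above 1.5 and below 1.7;
- an INR rise after screening in a patient already anticoagulated;
- an anticoagulant started during the study. Sections 6.6 and 6.7 do not prohibit anticoagulants, and 6.7 names warfarin as a drug to use with caution.

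**3. Weight of one patient**

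Input: 22 enrolled per arm (SAP 8.1). The range of 60 to 70 enrolled gives 60/3 = 20 to 70/3 ≈ 23 per arm.

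- 1/20 = 5.0 percentage points
- 1/22 = 4.5 percentage points
- 1/23 = 4.3 percentage points

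The table counts subjects, so each affected patient counts once in each treatment-period summary. The documents do not say how many patients are anticoagulated. If one to three per arm were affected (an assumption), the INR row would rise by 4.5 to 13.6 points at n = 22 (3/22 = 13.6%).

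**4. The >2×Baseline row**

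For two pre-dose values with ratio r, and taking the geometric mean in its usual sense, geometric mean / arithmetic mean = 2√r/(1+r). The SAP cut-off as a multiple of the protocol's baseline is twice that:

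| r | Ratio of means | SAP cut-off (protocol = 2.00) |
|---|---|---|
| 1.25 | 0.994 | 1.99 |
| 1.5 | 0.980 | 1.96 |
| 2 | 0.943 | 1.89 |
| 3 | 0.866 | 1.73 |

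Example: values of 40 and 60 give baselines of 50.0 (protocol) and 49.0 (SAP), hence cut-offs of 100.0 and 98.0. On the same two values the SAP cut-off is never the higher one. An unscheduled value can reverse this: 40, 70 (unscheduled) and 45 give a SAP baseline of (40×70×45)^(1/3) = 50.1 against (40+45)/2 = 42.5 under the protocol.

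**The case against.** The strongest reply is that nothing of consequence hangs on this table. AESI status comes from the investigator's CRF answer (SAP 10.7.7). AESIs go to a blinded committee and are summarised separately (SAP 12.6.2). The eDISH plot uses ALT/AST and bilirubin, not INR (SAP 12.6.4). In the protocol the four items are retest triggers, and reportable suspected DILI needs Criteria A, B or C. Concomitant medications and laboratory values are both listed by subject, so a careful reader could trace the cases. All of this stands, and it limits the point to a descriptive summary and a flag. It does not explain why a table under the suspected-DILI label should count patients whom the protocol exempts.

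A second reply is that removing these patients could hide a real effect. Protocol 1.1.4 reports that setanaxib 800 mg twice daily raised the AUC of a sensitive CYP2C9 probe by 45%, and section 6.7 warns of higher warfarin exposure. An INR rise in a warfarin user on setanaxib may therefore be related to the drug without being liver injury, and may be commoner in the active arms. This also stands. A reader might infer that the extra counts are noise unrelated to treatment; the documents do not support that. The values should be moved to their own row, not dropped.

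A third reply is that SAP 10.1.1 prespecifies the ALT/AST baseline openly. It does, and the effect is small: about 0.6% to 6% on the cut-off when the pre-dose values differ by a factor of 1.25 to 2. It can also go either way. A reader might take the baseline as an equal cause of miscounting; the arithmetic does not support that.

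**Conclusion.** The discrepancy is real and undeclared, and minor. Followed as written, SAP 12.6.3 counts and flags under suspected DILI an anticoagulated patient whose only finding is a post-baseline INR above 1.5, contrary to Protocol 5.3.2.1 and Appendix II. The size is 4.5 points of a 22-patient arm per affected patient. The total effect is unknown because the number of such patients is not given, and it could be zero.

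Two stronger readings should be avoided. One is that exclusion 7 admits anticoagulated patients at any INR, so that fully anticoagulated patients fill the table from the start. The Child-Pugh limit in exclusion 3, read plainly, bars a screening INR of 1.7 or more. If its anticoagulant exception were read to cover Child-Pugh as well, the affected group would be wider. The other is that patients are misclassified as DILI cases, or are counted again at every visit. No case classification uses this table, and it counts each subject once per treatment period.

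**What to change.** - In SAP 12.6.3, add the protocol's anticoagulant exemption to the INR row and apply it to the listing flag, using the concomitant-medication data already recorded.
- Add a separate labelled row for INR >1.5 in patients on anticoagulant therapy, so that a possible interaction stays visible without being called suspected DILI.
- For the AST/ALT >2×Baseline row, use the protocol's DILI baseline (arithmetic mean of Screening and Day 1), or keep the geometric mean and declare it in SAP 6.1. If the protocol's baseline is used, state which screening value applies when there was a retest: SAP 10.1.1 drops Visit 1 in that case and the protocol is silent.

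The cost is one qualifier, one extra table row, an anticoagulant indicator derived from existing data, and one sentence on the baseline. No new data collection is needed and no efficacy analysis changes.
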